5.2.2 Surgical extrusion (Visit 2)

The principal investigator performed all the procedures following the modified technique described by Kahnberg. Under local anesthesia and after having removed the caries lesion, each tooth was gently luxated with thin elevators, which were placed no more than 1mm within the gingival margin to avoid damaging the cervical PDL cells. Subsequently, teeth were coronally positioned using thin forceps to expose sufficient supracrestal tooth structure and splinted for 4 weeks with a retainer. Post surgery, the patients were prescribed analgesics and antibiotics for 1 week, and instructed to rinse daily with 0.12% chlorhexidine and follow a soft diet for 2 weeks.

5.2.3 Endodontic therapy (Visit 3)

All the root canal treatment and retreatments were completed one month after the surgery.

5.2.4 Restorative treatment (Visit 4)

The biologic width of each tooth was left to reestablish itself for 2 months, after which the same operator (ML) restored the teeth with a composite build-up and a fiber glass-reinforced epoxy post (Exacto, Angelus, Londrina, PR, Brazil) (if required) and in the same appointment all the teeth were prepared for single crowns with horizontal preparations.

5.2.5 Post-surgical assessment (Visit 5)

Patients were recalled at 12 months post-surgery, when a cast model was taken for the post-operative digital scanning, and the following clinical and radiographic parameters were recorded:

A) Clinical parameters

- Percussion.
- Palpation.
- Periodontal probing depths.
- Gingival recession.

- Clinical attachment level.
- Bleeding on probing.
- Tooth mobility.
- Gingival papillae shape and height.
- Bleeding on probing.
- Plaque index.
- Gingival index.
- Soft tissue rebound (STR): measured in mm by superposing both pre-operative and post-operative scanned models of each patient using surgical planning software (Blue Sky Plan, Blue Sky Bio, Libertyville, IL, USA). Soft tissue rebound was measured by calculating the difference between the lowest point of the gingival margin of the pre-operative model and the lowest point of the gingival margin of the post-operative model.

B) Radiographic parameters

- Periapical healing (Rud score): based on any radiolucency surrounding the apical third of the root, as follows:
 - Complete: Reestablishment of the periodontal space and the hard lamina around the apex.
 - Incomplete (scar tissue): Decrease or alteration of the apical lesion with at least one of the following characteristics: the periphery of the radiolucency is irregular and may be demarcated by a compact bony margin; the radiolucency is located asymmetrically around the apex.
 - Uncertain: Radiolucency greater than twice the width of the periodontal space and surrounded by tissue resembling a hard lamina. Lesion with circular or semicircular periphery and located symmetrically around the apex.
 - Unsatisfactory: Increase or maintenance of the size of the lesion.

- Root resorption: based on the aspect of the transplant periodontal ligament, as follows:
 - Absence of root resorption: complete PDL healing with normal width of the PDL space around the whole root.
 - Inflammatory root resorption: radiolucency is observed all along the external root surface of the dentin.
 - Replacement resorption: resorption lacunae are filled with bone and the PDL space is missing.
- Crown-root ratio (mm).
- Marginal bone loss.

C) Patient's satisfaction

Each patient filled in a questionnaire based on a 10-cm visual analogue scale to assess their degree of satisfaction regarding the surgical procedure and the esthetic outcome; 0 indicated a complete satisfaction while 10 was entirely unsatisfactory.

5.2 Success assessment

The following criteria were evaluated to establish the success of the treatment:

- Normal function of the extruded tooth with physiologic mobility without pain or discomfort.
- Healthy periodontal tissue surrounding the extruded tooth with periodontal pockets < 4 mm.
- Normal appearance of the PDL around the extruded tooth with no signs of any progressive root resorption or marginal bone loss $> 25\%$.

STATISTIC ANALYSIS PLAN (SAP)

The sample size was calculated based on the STR variation, using as a reference the study of Arora et al., in which the mean STR reported at 6 months was 0.77 ± 0.58 mm after the crown lengthening. This measure corresponds to a large effect size ($d=1.3$). In the present study the sample size was calculated using one sample t-test, considering a relevant STR of 0.5 mm at 12 months and a dropout of 15%. Thus, the final sample consisted in 15 patients, for a power of 80%, and considering an effect size of $d = 0.85$.

The data contained in the follow-ups were entered into a database (Excel, Microsoft Corporation) for data analysis and preparation for the final report. All the variables were analyzed using a descriptive method (mean, %). Besides, Chi² test was used to find a statistical relation between pre-operative and post-operative marginal bone loss of the extruded teeth.

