2.1. Secondary objectives

Evaluate the following periodontal and radiographic parameters:

- Gingival papillae shape and height (Jemt index).
- Bleeding on probing (mm).
- Plaque index (Turesky index).
- Gingival index (Silness & Löe index).
- Clinical attachment level (mm).
- Tooth mobility (Miller classification).
- Crown-root ratio (mm).
- Periapical healing (Rud score).
- Root resorption.
- Marginal bone loss.
- Patient satisfaction.

3. Hypotheses

Null hypothesis (H0):

H₀1: Surgical extrusion is not a predictable treatment for the restoration of single rooted teeth.

H₀2: Surgical extrusion of single rooted teeth results in an unfavorable aesthetic outcome.

Alternative hypothesis (H1):

H₁1: Surgical extrusion is a predictable treatment for the restoration of single rooted teeth.

H₁2: Surgical extrusion of single rooted teeth results in a favorable aesthetic outcome.

4. Study design

This is an interventional, monocentric, single-group, prospective clinical study.

5. Methods

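### The stated 80% power is for detecting that some soft tissue rebound exists; neither it nor the planned descriptive mean can show that rebound is below the 0.5 mm the plan calls relevant

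*Combined protocol and SAP*

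**What the plan says.** Section 2.1 (main objectives) lists STR at 12 months or later as one of two main objectives, worded as something to evaluate and without a margin. Section 3 states the second alternative hypothesis (H1-2): "Surgical extrusion of single rooted teeth results in a favorable aesthetic outcome". It attaches no endpoint or threshold to it.

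The Statistic Analysis Plan takes its planning figures from a study of crown lengthening, in which "the mean STR reported at 6 months was 0.77 ± 0.58 mm after the crown lengthening", and describes this as an effect size of 1.3. It continues: "In the present study the sample size was calculated using one sample t-test, considering a relevant STR of 0.5 mm at 12 months", allows 15% dropout and gives the effect size for this study as 0.85. The result is stated as "Thus, the final sample consisted in 15 patients, for a power of 80" per cent. The null value, the significance level and the sidedness are not given.

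For the analysis itself, the SAP describes all variables by means and percentages. The only test it names is a Chi² test on marginal bone loss. No test or confidence interval is specified for STR.

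**The concern.** STR is the only variable used to size the study, so a reader will take the 80% as the study's ability to answer its STR question. In a study whose alternative hypotheses are that the treatment is predictable and aesthetically favourable, the reassuring STR result would be that rebound is small. The test behind the sample size addresses something else: whether mean rebound differs from zero. Rejecting that null shows that some rebound exists. Failing to reject it, in about 13 teeth, does not show that rebound is negligible.

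At stake is how the final STR result is read. A mean reported without an interval, next to a claim of 80% power, invites the conclusion that rebound is below the relevant size when the data may be compatible with 0.5 mm or more.

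**Working it through.** **Inputs.** From the SAP: reference mean 0.77 mm and SD 0.58 mm; relevant STR 0.5 mm; effect size d = 0.85; power 80%; dropout 15%; N = 15 patients. Assumed: two-sided 5% (one-sided 5% as sensitivity), normal data, and a range of true STR values, since the documents give no expected STR for surgical extrusion.

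**1. Which null the effect sizes imply.** 0.77 / 0.58 = 1.33, stated as 1.3. 0.5 / 0.58 = 0.86, stated as 0.85. Both are means divided by the SD with nothing subtracted, so the implied null is a mean STR of zero.

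**2. Reproducing the stated N.** Power of a one-sample t-test is taken from the noncentral t distribution with n − 1 degrees of freedom and noncentrality d√n. With d = 0.85 and two-sided 5%:

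- n = 12: 76.4%
- n = 13: noncentrality 0.85 × √13 = 3.06, power 80.3%

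So 13 evaluable are needed, and 13 × 1.15 = 14.95, which rounds to the stated 15. (Dividing by 0.85 gives 15.3, or 16.) One-sided 5% needs 11, or 13 after dropout, which does not give 15. Two-sided 5% is therefore the likely setting, though it remains an assumption.

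**3. Precision of the mean.** The 95% CI half-width is t × SD / √n.

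- n = 13: 2.179 × 0.58 / √13 = 2.179 × 0.161 = 0.35 mm
- n = 15: 2.145 × 0.58 / √15 = 2.145 × 0.150 = 0.32 mm

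If the observed SD is 0.58 and n = 13, zero is rejected when the observed mean exceeds about 0.35 mm. The upper limit falls below 0.5 mm only when the observed mean is below 0.50 − 0.35 = 0.15 mm. A mean between about 0.15 and 0.35 mm would be compatible both with no rebound and with rebound of the relevant size.

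**4. Power to place the upper 95% limit below 0.5 mm.** The same noncentral t calculation applies, with d = (0.5 − true mean) / 0.58. For example, at a true mean of 0.2 mm, d = 0.3 / 0.58 = 0.517.

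| Assumed true STR (mm) | 13 evaluable | 15 evaluable |
|---|---|---|
| 0 | 81% | 87% |
| 0.1 | 63% | 70% |
| 0.2 | 40% | 46% |
| 0.3 | 21% | 24% |
| 0.4 | 8% | 9% |

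**5. Sensitivity.** With one-sided 5% and 13 evaluable, the column becomes about 90%, 76%, 55%, 32% and 15%. At a true STR of 0.2 mm with 13 evaluable and two-sided 5%, power is 70% if the SD is 0.4 mm and 30% if it is 0.7 mm.

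**6. What non-significance against zero would mean.** With 13 evaluable and SD 0.58, a test against zero would be non-significant 60% of the time at a true STR of 0.3 mm and 37% of the time at 0.4 mm. The plan does not schedule this test for the analysis. The figures show only why a non-significant result should not be read as no rebound.

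**The case against.** The strongest reply is that STR is to be described, not tested. Its objective is one of evaluation, no STR p-value is planned, and nothing in the plan says that a non-significant result counts as favourable. The SAP presents 0.5 mm as a size worth detecting, not as an acceptance limit. All of this stands, and it rules out several stronger readings.

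- **That H1-2 requires rebound to be shown below 0.5 mm.** A reader might infer this because STR is a main objective and drives the sample size. No section links H1-2 to STR. The satisfaction scale in section 5.2.5 mentions the aesthetic outcome expressly, and the papilla index in section 5.2.1 is another candidate measure.
- **That rejecting zero would be an unfavourable result.** It would show only that mean rebound is not zero. An observed mean just above 0.35 mm can reject zero while lying below 0.5 mm.
- **That the study has 40% power for its favourable claim.** The 40% belongs to an assumed true STR of 0.2 mm, which is not in the documents. Only the range is defensible. If true STR is zero, the same 13 evaluable give 81%.

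The SD also comes from a different procedure at 6 months, and the unit is unclear: the SAP counts 15 patients, while section 5.1 has 14 patients with 15 teeth. These are reasons to treat the percentages as indicative.

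The reply does not rescue the stated power. A descriptive analysis uses no power figure, and a mean without an interval cannot separate negligible rebound from rebound of the relevant size.

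**Conclusion.** The point holds in limited form. The 80% is power to reject a mean STR of zero when true rebound is 0.5 mm; 80.3% with 13 evaluable reproduces it under two-sided 5%. It is not power to show that rebound is smaller than 0.5 mm, and the planned descriptive mean cannot show that either. The stated power therefore supports no favourable conclusion drawn from STR.

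With SD 0.58 and 13 evaluable, the power to exclude 0.5 mm from above falls from 81% at zero true rebound to 8% at 0.4 mm; with 15 evaluable it falls from 87% to 9%. This rests on the assumed significance level, the borrowed SD, one independent measurement per unit, and the use of the plan's 0.5 mm as the benchmark.

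The finding concerns what the sample size can support. It does not establish that the plan intends to claim success from a non-significant test, or that H1-2 is an STR hypothesis.

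**What to change.** In the SAP:

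1. State that the 80% power is against a null of zero mean rebound, and give the significance level and sidedness used.
2. Report mean STR with its SD and a two-sided 95% CI, and define the sign. Section 5.2.5 defines STR as a difference between two gingival margin positions without saying which direction is positive, and a reading against an upper limit depends on it.
3. Say that rebound is below the relevant size only if the upper confidence limit is below 0.5 mm, and that a non-significant difference from zero is not evidence of no rebound.
4. If H1-2 is to rest on STR, say so and give the power as the range in the table above, not as a single 80%. If it is to rest on another measure, name that measure and its criterion.

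The cost is a few sentences of SAP wording and a less favourable stated power. No extra patients are needed for these changes. They make clear what the present sample can show and do not raise its power.

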TITLE OF THE STUDY: Surgical extrusion for the clinical crown lengthening: a 12-months prospective clinical study

RESEARCH ETHICAL COMMITTEE APROVAL DATE:
15 March 2018

PROTOCOL

1. Scientific background:

Long-term survival rates of restorations after endodontic treatment range between 81% and 100%. Outcome predictors for the restored tooth with a prosthetic crown mainly include cavity wall integrity and the presence of 1.5 to 2 mm of ferrule (360 degrees sound dentin collar). In some clinical situations, the aforementioned requirements cannot be achieved, especially in deep carious lesions, cervical perforations, crown-root fractures, and failed crowns with preexisting subgingival margins. In such cases, ferrule should not be provided at the expense of the remaining tooth structure since it may provoke a biologic width invasion and, consequently, a chronic gingival inflammation and a loss of soft tissue and bone.

Three treatment options aim to obtain adequate ferrule while respecting the biologic width: surgical crown lengthening, rapid orthodontic extrusion and surgical extrusion. Surgical crown lengthening involves the removal of hard and soft tissue for the exposure of sufficient supragingival tooth structure. Rapid orthodontic extrusion, which is a less invasive treatment, allows the preservation of periodontal tissues. However, it is necessary to consider the patient's willingness to wear orthodontic appliances, which increases the cost and time of the therapy. Surgical extrusion consists in atraumatic luxation of the tooth to enable its coronal reposition. Several authors have reported survival rates higher than 95% on surgical extrusion. However, little prospective studies are available in relation to the periodontal changes after SE.

2. Objectives:

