5.2 Treatment plan

5.2.1 Pre-surgical assessment (Visit 1)

On the first appointment, patient's medical and dental history was reviewed. Patients age, sex and tooth number were recorded. A pre-operative cast model of each extruded tooth was taken and digitally scanned to assess the STR. Also, patient's biotype (De Rouck) was registered based on the transparency of the periodontal probe through the gingival margin while probing the buccal sulcus, as follows:

- 0: Both upper central incisors have thin biotype.
- 1: One of the two upper central incisors has a thin biotype.
- 2: Both upper central incisors have thick biotype.

A) Clinical parameters

- Percussion: assessed with a mirror handle in a vertical direction.
- Palpation: assessed by a gentle finger pressure on both buccal and palatal soft tissue around the transplant.
- Periodontal variables, using an standardized manual periodontal probe PCP-UNC 15 (Hu-Friedy®, [name]):
 - Periodontal probing depths (PPD): measured at 6 sites per tooth. Defined as the distance, in millimeters, from the gingival margin to the bottom of the probable pocket.
 - Gingival recession: measured at 6 sites per tooth. Defined as the distance, in millimeters, from the cementoenamel junction (CEJ) to the gingival margin.
 - Clinical attachment level (CAL): calculated indirectly as the sum of the previously recorded PPD and gingival recession, representing the distance between the CEJ and the bottom of the pocket on all present teeth.
 - Bleeding on probing (BoP): recorded dichotomously, at six sites, as present or absent within 15 seconds after the direct assessment of PPD, at six aspects of each tooth.
- Tooth mobility (Miller classification): measured using two dental mirror handles.
 - Grade 0: Normal (physiologic) movement when force is applied.
 - Grade 1: Mobility greater than physiologic.
 - Grade 2: Tooth can be moved up to 1mm or more in a lateral direction (buccolingual or mesiodistal). Inability to move the tooth in a vertical direction (apicocoronally).

- Grade 3: Tooth can be moved 1mm or more in a lateral direction (buccolingually or mesiodistally). Ability to move the tooth in a vertical direction.
- Gingival papillae shape and height (Jemt index): based on the distance from the highest curvature of the marginal buccal gingiva to the contact point of the transplanted tooth with the following index scores:
 - 0 No papilla is present.

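### Apart from STR and the Chi² test on bone loss, the SAP plans no per-tooth change, with SD or CI, for the periodontal measures taken at both visits

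*Combined protocol and SAP*

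**What the plan says.** Section 1 motivates the study partly by a gap in evidence: "little prospective studies are available in relation to the periodontal changes after SE". The secondary objectives then list bleeding on probing, plaque index, gingival index, attachment level, mobility and papilla index, among others.

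Section 5.2.1 takes these at Visit 1, some of them site by site: "Periodontal probing depths (PPD): measured at 6 sites per tooth", and likewise recession and bleeding. Section 5.2.5 repeats the set at Visit 5: "Patients were recalled at 12 months post-surgery, when a cast model was taken for the post-operative digital scanning". Its list for that visit names the same periodontal items again.

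The SAP covers all of this in one sentence: "All the variables were analyzed using a descriptive method (mean", followed by a percent sign as the only other summary. The next sentence adds a single pre/post analysis: "Chi² test was used to find a statistical relation between pre-operative and post-operative marginal bone loss of the extruded teeth". The sample-size paragraph allows for "a dropout of 15" per cent. The SAP states no rule for teeth without a 12-month visit.

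**The concern.** In a single-group study each tooth is its own and only comparator. The baseline values are collected, but the SAP gives them no role as the starting point for each tooth, apart from STR and bone loss. Two things are at stake.

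- **Precision and direction of change.** A reader given one summary per visit cannot tell how variable the change was, how precisely its mean is known, or whether a stable percentage hides some teeth getting worse while others improve.
- **Which teeth are compared.** If any tooth lacks the 12-month visit and each summary uses whatever is available, the difference between visits mixes change with a difference in who was measured.

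**Working it through.** **The plan's own figure.** The SAP's 15 reproduces. A one-sample t-test with d = 0.85, 80% power and alpha 0.05 two-sided (alpha and sidedness are assumed; the SAP gives neither) needs 13 units, with power 80.3%. Then 13 x 1.15 = 14.95, rounded up to 15; dividing instead, 13/0.85 = 15.3, gives 16. This sizes the study for STR only, and the point below does not depend on it.

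**Inputs from the documents.** 15 teeth in 14 patients (section 5.1); 15% dropout allowance, 0.5 mm as the relevant STR, and SD 0.58 mm for STR from the reference study (SAP). **Assumed:** within-tooth correlation rho from 0.3 to 0.7, equal SD s at both visits, and baseline gap D from 0.5 to 2 mm.

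**Step 1: complete follow-up, mean change.** With the same 15 teeth at both visits, mean(Visit 5) - mean(Visit 1) = mean(Visit 5 - Visit 1) exactly. The point estimate is therefore derivable.

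**Step 2: complete follow-up, precision.** The 95% half-width for the mean change is t(0.975, n-1) x SD of change / √n. It is 0.55 SD of change for n = 15 and 0.60 for n = 13. Borrowing 0.58 mm as the SD of change, purely for illustration, gives 0.32 and 0.35 mm.

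The SD of change cannot be obtained from visit means. Visit SDs, which the SAP does not name either, would not be enough, because SD of change = s x √(2(1 - rho)) and rho is not reported. The half-width in units of s would be:

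| Teeth | rho = 0.3 | rho = 0.5 | rho = 0.7 | Visits treated as independent |
|---|---|---|---|---|
| 15 | 0.66 | 0.55 | 0.43 | 0.75 |
| 13 | 0.72 | 0.60 | 0.47 | 0.81 |

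The last column is t(0.975, 2n-2) x √(2/n). The plan proposes no such interval; the column shows what a reader would have to fall back on.

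**Step 3: graded scores.** Suppose 3 of 15 teeth (20%) have mobility Grade 1 at each visit. Those percentages fit no tooth changing. They fit equally well three teeth worsening and three others improving.

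**Step 4: if teeth are lost.** 15% of 15 is 2.25, so about 2 teeth. Let the 13 retained teeth have baseline mean m, the 2 lost teeth m + D, and let no tooth change. The Visit 1 mean over 15 is m + (2/15)D and the Visit 5 mean over 13 is m. The apparent change is -(2/15)D:

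- D = 0.5 mm: 0.07 mm
- D = 1 mm: 0.13 mm
- D = 2 mm: 0.27 mm

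For scale, 0.13/0.5 = 27% of the difference the SAP calls relevant, although that threshold is for STR. With no loss, or D = 0, the shift is zero.

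**The case against.** The strongest reply is that these are secondary, descriptive outcomes in a small study, that the secondary objective is to evaluate the parameters and not to estimate change, and that neither main objective is touched. That is fair and limits the weight of the point. It does not remove it, because the background gives periodontal change as the gap and the measures are taken twice.

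Three stronger readings are tempting, and the documents do not support them.

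- **A reader might infer that within-tooth change is never estimated.** STR is itself such a change, "measured in mm by superposing both pre-operative and post-operative scanned models of each patient", and by Step 1 the mean change in the other continuous measures follows from the visit means when all teeth are seen. The SAP is silent on change scores; it does not exclude them.
- **A reader might infer that the SAP uses means and percentages alone.** It also has the Chi² test. That test concerns one radiographic variable and is not a paired analysis, so it does not fill the gap for the clinical measures.
- **A reader might infer that the two visit means do describe different teeth, or that a spurious change will appear.** The 15% is a planning allowance and the documents report no actual loss. A shift also needs the lost teeth to differ at baseline. A 2 mm gap is an upper scenario with no source in the documents, and the sample is restricted to periodontally healthy patients.

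It is also right that a formal test on mobility would add little: Grades 2 and 3 are excluded at entry, so improvement can be at most one grade, and ties would leave few informative teeth.

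**Conclusion.** The point holds as a limited one. For probing depth, attachment level, bleeding, gingival index, plaque index, papilla index and mobility, the SAP plans no per-tooth change with a measure of spread or precision, and does not tie the two visit summaries to the same teeth. Even with full follow-up, the SD and CI of the change, and the number of teeth that worsened or improved, cannot be recovered from what is planned. The possible distortion from loss is conditional: it rests on two lost teeth and an assumed baseline gap, and vanishes without either. The precision figures rest on an assumed correlation and equal SDs. The success rate and STR are unaffected. This is a worthwhile improvement at almost no cost, not a flaw that undermines the main results.

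**What to change.** Add to the SAP:

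- For probing depth, attachment level, bleeding on probing (percent of the six sites), gingival index and plaque index: define 12 months minus Visit 1 within each tooth, after reducing site readings to one value per tooth. Report n, mean, SD and 95% CI in teeth seen at both visits.
- For mobility and papilla index: report the number of teeth improved, unchanged and worsened. No test is needed.
- List the Visit 1 values of any tooth without a 12-month visit.
- State that 14 patients contribute 15 teeth, and repeat the CIs with one tooth per patient. With 14 teeth the half-width is 2.160/√14 = 0.58 SD of change, against 0.55 with 15, so little precision is lost.

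The cost is a few lines of SAP text and minor analysis work. The schedule already collects every value needed, and the sample size does not change.

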5.1 Study population

This prospective study comprises 14 consecutive patients in whom 15 single-rooted teeth were surgically extruded at the Department of Endodontics at International University of Catalonia, St Cugat del Vallès, Barcelona, Spain. The sample was recruited according to the following inclusion and exclusion criteria:

Inclusion criteria:

- Systemically and periodontally healthy, non-smoking patients.
- Single-rooted, straight teeth with insufficient ferrule, which require restorative treatment.
- Teeth with a favorable crown-root ratio.

Exclusion Criteria:

- Severe systemic disease patients (American Society of Anesthesiologists classification 1 or 2).
- Multi-rooted, curved and/or short teeth.
- Teeth with an uncontrolled periodontal pathology.
- Pregnant women.
- Teeth with types II or III mobility.

All included patients signed an informed consent, and the study was approved by the Ethics Committee of Investigation of the Universitat Internacional de Catalunya (END - ECL – 2017 - 02).

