 - 1 Less than half of the height of the papilla is present.
 - 2 Half or more of the height of the papilla is present but does not extend all the way up to the contact point between the teeth.
 - 3 The papilla fills up the entire proximal space and is in good harmony with the adjacent papillae. There is optimal soft tissue contour.
 - The papilla is hyperplastic and covers too much of the transplanted or adjacent tooth. The soft tissue contour is more or less irregular.
- Bleeding on probing (mm): recorded dichotomously as present or absent within 15 seconds after the assessment of PPD, at six aspects of each transplant.
- Plaque index (Turesky index): visually measured as follows:
 - 0: No plaque present
 - 1: Separate flecks of plaque at the cervical margin.
 - 2: A thin continuous back of plaque (up to 1 mm) at the cervical margin.
 - 3: A band of plaque wider than 1 mm but covering less than one-third of the surface.
 - 4: Plaque covering at least one-third but less than two-thirds of the surface.
 - 5: Plaque covering more than two-thirds of the surface.

- Gingival index (Silness & Löe index): the scores of the four areas of the tooth can be summed and divided by four to give the GI for the tooth.
 - Score 0 = Normal gingiva.
 - Score 1 = Mild inflammation - slight change in color, slight edema. No bleeding on probing.
 - Score 2 = Moderate inflammation - redness, edema, glazing. Bleeding on probing.
 - Score 3 = Severe inflammation - marked redness and edema, ulceration. Tendency toward spontaneous bleeding.

B) 2D radiographic parameters

Standardized digital bitewings and periapical radiographs with paralleling technique (Kodak RVG 6100; Carestream Health, Rochester, NY) and a selective CBCT scan (CS 9300; Carestream Health, set at 8.0 mA and 84 kV, with a 12-second exposure time and the smallest possible field of view (5 x 5 cm) were taken to assess root anatomy as well as the following radiographic parameters:

- Preoperative periapical lesion, recorded dichotomously as present or absent from the periapical radiography.
- Crown-root ratio (mm): measured on the periapical radiograph, and scored as follows:
 - Good: crown-root ratio < 1.
 - Just: crown-root ratio = 1.
 - Unfavorable: crown-root ratio > 1.
- Marginal bone loss: based on the bone crest aspect on the bitewing radiograph, as follows:
 - Initial: < 25% of marginal bone loss.
 - Moderate: between 25% - 50% of marginal bone loss.
 - Severe: > 50% of marginal bone loss.

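### The SAP's only listed test, a Chi² on marginal bone loss before and after surgery in the same teeth, does not test whether bone was lost

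*Combined protocol and SAP*

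**What the plan says.** Section 2.1 (Secondary objectives) includes marginal bone loss under the instruction "Evaluate the following periodontal and radiographic parameters". Section 5.2.1 B grades it from the bitewing radiograph in three ordered steps. Initial is below 25%, the middle step is "Moderate: between 25% - 50% of marginal bone loss", and Severe is above 50%. Section 5.2.5 repeats the reading on the same teeth: "Patients were recalled at 12 months post-surgery". Section 5.1 gives the units as "14 consecutive patients in whom 15 single-rooted teeth were surgically extruded", and the entry criteria ask for "Systemically and periodontally healthy, non-smoking patients".

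The SAP summarises all variables by means and percentages and adds one test, a Chi² that "test was used to find a statistical relation between pre-operative and post-operative marginal bone loss of the extruded teeth". It does not give the layout of the table, an exact method, a significance level, or a paired test for bone loss. The one-sample t-test on soft tissue rebound is a within-tooth comparison, but the SAP names it only for the sample size.

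**The concern.** Each tooth supplies both readings, so the data are 15 matched pairs of ordered grades. The question that follows from the objective is whether teeth moved to a worse grade. A Chi² on the cross-table of earlier by later grade has independence of the two grades as its null hypothesis. Grades of the same tooth 12 months apart are expected to be related, so rejecting independence says nothing about bone loss. A Chi² on a stacked before/after table does compare the two distributions, but it discards the pairing. Neither layout uses the order of the grades.

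This would be the only p-value from the listed analyses, and it concerns a possible harm of the procedure. A reader could take a significant result as evidence of bone loss, or a non-significant one as reassurance. Neither inference would be sound.

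**Working it through.** **Inputs.** There are 15 teeth (section 5.1), three ordered grades (section 5.2.1 B) and two readings per tooth (sections 5.2.1 and 5.2.5). The documents give no grade counts, so every table below is illustrative and assumes 15 complete pairs. The plan states no figure for this test. Its one calculated figure, N = 15, concerns soft tissue rebound. It reproduces (13 teeth for d = 0.85 at two-sided 5% and 80% power; 13 × 1.15 = 14.95, rounded up to 15) but has no bearing here.

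**Formulas.** For a 2×2 table with cells a, b, c, d and total N, Pearson χ² = N(ad − bc)² / (product of the four margins), on 1 degree of freedom. With k teeth changing in one direction and none in the other, the exact McNemar (sign) test gives p = 2 × 0.5^k.

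**Reading 1: earlier grade by later grade, N = 15.**

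No tooth changes, 10 Initial and 5 Moderate: χ² = 15 × (10×5 − 0)² / (10×5×10×5) = 37,500 / 2,500 = 15.0. With two grades present and no change, χ² always equals N.

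Six of the 10 Initial teeth worsen and the 5 Moderate teeth stay: χ² = 15 × (4×5 − 6×0)² / (10×5×4×11) = 6,000 / 2,200 = 2.73.

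| Initial/Moderate before surgery | Change | Pearson p | Yates p | Fisher p | Exact McNemar p |
|---|---|---|---|---|---|
| 10/5 | none | 0.0001 | 0.001 | 0.0003 | 1 |
| 13/2 | none | 0.0001 | 0.006 | 0.010 | 1 |
| 14/1 | none | 0.0001 | 0.072 | 0.067 | 1 |
| 15/0 | none | not computable | – | – | 1 |
| 10/5 | 6 Initial worsen | 0.099 | 0.30 | 0.23 | 2 × 0.5⁶ = 0.031 |
| 13/2 | 6 Initial worsen | 0.16 | 0.51 | 0.47 | 0.031 |

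Two further checks on this reading:
- If all 15 teeth in the 10/5 split worsen by one grade, χ² is again 15.0, exactly as when none changes. The exact sign test gives 2 × 0.5¹⁵ = 0.00006.
- The smallest expected counts at 10/5 are 5×5/15 = 1.67 (no change) and 5×4/15 = 1.33 (six worsen), so the uncorrected large-sample p-value is unreliable as well.

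A simulation (4,000 runs per setting) used assumed grade probabilities of 0.6/0.3/0.1 and no overall change. The cross-table Chi² was significant at 5% in 5%, 59% and 96% of runs when the share of teeth keeping their grade by design was 0, 0.5 and 0.8. The exact sign test rejected in at most 2.4%.

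**Reading 2: before and after stacked, N = 30.**

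Six of 10 worsen: χ² = 30 × (10×11 − 5×4)² / (15×15×14×16) = 243,000 / 50,400 = 4.82. Five of 15 worsen from all Initial: χ² = 30 × (15×5 − 0)² / (15×15×25×5) = 168,750 / 28,125 = 6.0.

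| Initial/Moderate before surgery | Change | Pearson p | Yates p | Fisher p | Exact McNemar p |
|---|---|---|---|---|---|
| 10/5 | none | 1 | – | – | 1 |
| 10/5 | 6 Initial worsen | 0.028 | 0.067 | 0.066 | 0.031 |
| 15/0 | 5 worsen | 0.014 | 0.050 | 0.042 | 2 × 0.5⁵ = 0.063 |

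This layout does not produce significance when nothing changes. In the same simulation it rejected in 0.4% and 0.0% of runs at shares of 0.5 and 0.8, which is too conservative.

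**Proposed summary (Clopper-Pearson 95% interval).** For 0 of 15 worsened, the upper limit is 1 − 0.025^(1/15) = 21.8%, so the interval is 0 to 21.8%. For 5 of 15 it is 11.8% to 61.6%.

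**The case against.** The SAP speaks of a relation, not of change, so on its literal wording a Chi² for association could be called the right test. Even so, no stated objective asks whether later grades are associated with earlier ones, and the result would not show whether bone was lost.

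The term could also loosely mean McNemar's chi-squared, or a stacked table. Nothing in the text says McNemar. The stacked reading is a smaller error, and at 10/5 with six worsening it nearly matches the paired result (0.028 against 0.031). A plan open to three readings still has to say which is meant.

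The starkest figures need several teeth with at least 25% bone loss at entry, which sits uneasily with periodontally healthy patients. This objection stands in part. At 14/1 the corrected and exact p-values are not significant, and at 15/0 there is no p-value to mislead anyone. But in that last case the SAP's one planned test yields nothing.

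The remedy partly exists already, since bone loss above 25% is a success criterion and the grades will be described as percentages. That is also fair. What is missing is a separate count of worsened teeth with its uncertainty. With 15 teeth, at least six one-way changes are needed for two-sided p < 0.05, so any test adds little to that count. That is a reason to put the count and its interval first.

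**Conclusion.** The concern holds. On the literal cross-table reading, the Chi² does not test change. It can be strongly significant when no tooth changed (p = 0.0001 at 10/5), non-significant when six teeth worsened (p = 0.099 against an exact paired 0.031), and impossible to compute when all teeth start as Initial. On the stacked reading the fault is smaller: the pairing is ignored, and p can be too small (0.014 against 0.063) or too conservative. That the Chi² does not suit paired ordered grades follows from the design and does not depend on any counts. The size of the discrepancy rests on assumed baseline splits and 15 complete pairs.

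The analysis should be corrected, but the consequence is limited. Marginal bone loss is a secondary parameter, it is also described in percentages, and this p-value enters neither the success classification nor the soft tissue rebound result.

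**What to change.** Replace the Chi² sentence in the SAP with the following:
- **Main summary:** the number of teeth whose grade worsened between baseline and 12 months, with an exact 95% confidence interval, shown beside the table of earlier by later grade. For teeth that start as Initial, this is the number that crossed the 25% line.
- **Supporting test:** an exact sign or Wilcoxon signed-rank test on the grade change, which keeps its direction, or an exact McNemar test at the 25% cut. If all teeth start as Initial, none can improve on this scale, so rely on the count and its interval.
- **Missing data:** use teeth with both readings and state how many are missing.
- **Optional:** a sensitivity analysis with one tooth per patient, since 15 teeth come from 14 patients.

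The cost is one or two sentences. The paired grades are already part of the data collection, so no new measurement is needed.
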